- ITT3_A: The subset of ITT3 who were the first 450 upadacitinib 45 mg QD 8-week induction responders and who were enrolled under the protocol for 52-week maintenance treatment period in Cohort 1. The ITT3_A is the primary analysis population in Cohort 1 for efficacy endpoints.
- ITT3_B: The subset of ITT3 in Cohort 3 who were upadacitinib 45 mg QD 16-week induction responders.
- ITT3_C: The subset of ITT3 who were enrolled under the original protocol, Amendment 1 or 2 for 44-week maintenance treatment period.
- ITT3_D: The subset of ITT3 who were upadacitinib 45 mg QD 8-week induction responders and who were enrolled under the protocol for 52-week maintenance treatment period in Cohort 1.
- ITT3_E: The subset of ITT3 who were placebo, upadacitinib 7.5 mg QD, 15 mg QD or 30 mg QD 8-week induction responders and who were enrolled under the protocol for 52-week maintenance treatment period.

Primary analysis and secondary analyses of Substudy 3 will be performed for ITT3_A, ITT3_B, ITT3_C and ITT3_E.

The comparison between treatment groups in ITT3_A population for the primary efficacy endpoint will be performed using the CMH test and will be stratified by previous bio-IR status (yes or no), clinical remission status at Week 0 (yes or no), and corticosteroid use at Week 0 (yes or no). Non-responder imputation incorporating multiple imputation to handle COVID-19 (NRI-C) method will be used for the primary analysis.

Additional analyses are outlined in the protocol.

Pharmacokinetic:

Individual plasma concentrations of upadacitinib will be tabulated and summarized. A non-linear mixed-effects modeling approach will be used to estimate the population central values and the empirical Bayesian estimates of the individual values for upadacitinib oral clearance (CL/F) and volume of distribution (V/F). Additional parameters may be estimated if useful in the interpretation of the data.

Statistical Methods (Continued):

Safety:

Safety analyses will be carried out using the safety analysis set in Substudies 1 to 3, which includes all subjects who receive at least one dose of study medication in each portion of the study, respectively. Incidence of adverse events, changes in vital signs, physical examination results, ECGs, and clinical laboratory values will be analyzed. Treatment-emergent adverse events will be tabulated by system organ class and by MedDRA preferred term for each treatment group for each Substudy and over the entire study. Mean change from Baseline for laboratory and vital signs data will be summarized.

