8.1.1.2 Safety Analysis Set

The safety analysis set in each substudy consists of all subjects who received at least one dose of study medication in each portion of the study, respectively. For the safety analysis sets, subjects are assigned to a treatment group based on the treatment actually received, regardless the treatment randomized. Safety analyses of Substudy 1 to 3 will be carried out using the corresponding safety analysis set. Safety analyses of the entire study will be carried out using the union of all safety analysis sets for all treated subjects.

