8.1.5.2 Study Drug Exposure

Exposure to study drug will be summarized for all subjects who have received at least one dose of study drug for each substudy and over the entire study. The duration (days) of study drug treatment will be summarized with the mean, standard deviation, median and range for each treatment group. The duration of treatment is defined as the difference between the dates of the first and last doses of the treatment plus 1 day. Study drug compliance will be summarized for each treatment group. Compliance is defined as the number of tablets taken (i.e., the difference between the number of tablets dispensed and the number of tablets returned) divided by the number of tablets a subject is supposed to take each day times the length of time that the subject was in the Treatment Phase of the

study (i.e., Final/Discontinuation Visit date during Treatment Phase – Day 1 [Baseline] Visit date +1). Subjects with missing data for the number of tablets returned will be excluded from the summary.

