8.1.8 Safety Analysis

8.1.8.1 General Considerations

Safety analysis in Substudies 1 to 3 will be carried out using the corresponding safety analysis set. For the safety analysis of the entire study (Substudy 1, Substudy 2, and Substudy 3), all treated subjects will be included. Incidence of adverse events, including those related to study drug, changes in vital signs, physical examination results, ECGs, and clinical laboratory values will be analyzed.

Treatment-emergent AEs are defined as events that begin or worsen either on or after the first dose of the study medication and within 30 days after the last dose of the study medication. AEs will be summarized for each substudy and through the entire study. An overview of treatment-emergent AEs, including AEs of special interest such as adverse events leading to death and adverse events leading to early termination (see details in the SAP), AEs by Medical Dictionary for Regulatory Activities (MedDRA) preferred term

and system organ class, AEs by maximum relationship to study drug, and AEs by maximum severity will be summarized by number and percentage.

Changes in laboratory data will be described using statistical characteristics and comparison between treatment groups will be performed using a one-way Analysis of Variance (ANOVA). In addition, shift tables and listings will be provided for abnormal values, whereby the normal range of the analyzing laboratory will be used. Vital signs will be analyzed similarly.

Missing safety data will not be imputed.

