9.2.1 Treatment-Emergent Adverse Events

The Treatment-Emergent Adverse Events (TEAEs) for SA (SA_A, SA_B, SA_C and SA_D) and SA_UPA populations are defined as follows.

SA (SA_A, SA_B, SA_C and SA_D) population: TEAEs are defined as events that begin either on or after the first dose of the study drug in the Maintenance Study and

- within 30 days after the last dose administration of the study drug for subjects who do not participate in the long-term extension Study M14-533 or
- until first dose of study drug in the Study M14-533 if the subject is enrolled into Study M14-533

SA_UPA population: TEAEs are defined as events that begin either on or after the first dose of upadacitinib study drug in Maintenance Study and

- within 30 days after the last dose administration of the study drug for subjects who do not participate in the long-term extension Study M14-533 or
- until first dose of study drug in the Study M14-533 if the subject is enrolled into Study M14-533

If an incomplete onset date was collected for an adverse event, the event will be assumed to be treatment-emergent unless there is other evidence that confirms that the event was not treatment-emergent (e.g., the event end date was prior to the study drug start date). The number and percentage of subjects experiencing treatment-emergent AEs will be summarized.

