10.0 Other Analyses

No other analyses are planned.

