9.2.1 Treatment-Emergent Adverse Events

The Treatment-Emergent Adverse Events (TEAEs) for SA1, SA2 and the SA-UPA populations are defined as follows.

Part 1 (SA1 population): TEAEs for Part 1 are defined as events that begin either on or after the first dose of the study drug in Part 1 and

- until first dose of study drug in Part 2 if the subject is enrolled into Part 2 or
- until first dose of study drug in the Maintenance Study if the subject is enrolled into the Maintenance Study or
- within 30 days after the last dose administration of the study drug for subjects who are not enrolled in Part 2 and do not participate in the Maintenance Study.

Part 2 (SA2 population): TEAEs for Part 2 are defined as events that begin either on or after the first dose of OL upadacitinib study drug in Part 2 and

- until first dose of study drug in the Maintenance Study if the subject is enrolled into the Maintenance Study or
- within 30 days after the last dose administration of the study drug for subjects who do not participate in the Maintenance Study.

SA–UPA population: TEAEs are defined as events that begin either on or after the first dose of upadacitinib study drug in either Part 1 or Part 2 and

- until first dose of study drug in the Maintenance Study if the subject is enrolled into the Maintenance Study or
- within 30 days after the last dose administration of the study drug in Part 1 for subjects who are not enrolled in Part 2 and do not participate in the Maintenance Study or
- within 30 days after the last dose of the study drug in Part 2 for subjects who are enrolled in Part 2 and do not participate in the Maintenance Study.

If an incomplete onset date was collected for an adverse event, the event will be assumed to be treatment-emergent unless there is other evidence that confirms that the event was not treatment-emergent (e.g., the event end date was prior to the study drug start date). The number and percentage of subjects experiencing treatment-emergent AEs will be summarized.

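### The protocol commits to safety and exposure summaries over the entire study, but no SAP specifies them, and events soon after 45 mg in responders re-randomised to placebo enter no upadacitinib set

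*Protocol*

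**What the plan says.** **Protocol.** Four places commit to results that span the substudies:

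- Section 1.2 (Synopsis, Safety): adverse events are tabulated "by MedDRA preferred term for each treatment group for each Substudy and over the entire study".
- Section 8.1.1.2: "Safety analyses of the entire study will be carried out using the union of all safety analysis sets for all treated subjects".
- Section 8.1.5.2: exposure is summarised for subjects with "at least one dose of study drug for each substudy and over the entire study".
- Section 8.1.8.1: "AEs will be summarized for each substudy and through the entire study", and "For the safety analysis of the entire study (Substudy 1, Substudy 2, and Substudy 3), all treated subjects will be included".

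Section 8.1 places the full analysis details in the SAP of each substudy.

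**SAPs.** The safety set in the Substudy 1 SAP (Section 5.1) is limited to Substudy 1. In the Substudy 2 SAP (Section 4.0) the widest upadacitinib set, SA-UPA, covers Parts 1 and 2 of that substudy. In the Substudy 3 SAP (Section 4.0) the widest upadacitinib set, SA_UPA, requires a dose of upadacitinib in the Maintenance Study, and its events are "events that begin either on or after the first dose of upadacitinib study drug in Maintenance Study". Section 10.0 of both Phase 3 SAPs states: "No other analyses are planned".

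**Event windows.** For a Substudy 2 subject who goes on to maintenance, the induction window runs "until first dose of study drug in the Maintenance Study if the subject is enrolled into the Maintenance Study or" (the list then turns to other subjects). The Substudy 1 SAP (Section 11.2.1) closes its window at the same point. The Substudy 3 window (Section 9.2.1) opens at the first maintenance dose.

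**The concern.** Section 1.0 of both the Substudy 2 and the Substudy 3 SAP says that changes to the protocol's analyses are outlined in Section 13.0. Neither version history mentions dropping the entire-study safety analysis. A programmer who follows the SAPs would omit an analysis that the protocol promises four times, and the record would not show that anyone decided to omit it.

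Without that analysis, rates per 100 patient-years are specified only within each substudy. No table follows a subject's upadacitinib exposure from induction into maintenance.

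The switch of windows adds an attribution problem. A responder who takes 45 mg up to the end of induction, is re-randomised to placebo and has an event on day 10 is counted as maintenance placebo. A Part 2 subject who finishes the same 45 mg course without going on to maintenance keeps a 30-day tail under induction (Substudy 2 SAP, Section 9.2.1). Events equally close to the last 45 mg dose are thus attributed differently. The placebo arm concerned is the comparator for the event differences with 95% confidence intervals that Section 9.2.2 of the Substudy 3 SAP plans for SA_A and SA_C.

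**Working it through.** The plan states no figure to reproduce. The main check sets the commitments beside the SAPs. The arithmetic only sizes the attribution point.

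**1. Commitment against specification**

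| Source | Scope |
|---|---|
| Protocol 1.2, 8.1.1.2, 8.1.5.2, 8.1.8.1 | Each substudy and the entire study |
| Substudy 1 SAP 5.1, 9.0, 11.2.1 | Substudy 1 |
| Substudy 2 SAP 4.0, 6.0, 9.2 | Substudy 2, Parts 1 and 2 |
| Substudy 3 SAP 4.0, 6.0, 9.2 | Maintenance Study |

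The entire-study analysis is promised in four places and found in none of the three SAPs.

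**2. Where events after the last induction dose go**

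Week 0 of maintenance falls on the day of the final induction visit (Protocol Section 5.1.2; Substudy 3 SAP Section 2.2), so there is no gap between the windows.

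- 45 mg responder re-randomised to 15 or 30 mg (Cohort 1, or Cohort 3, which has no placebo arm): counted under maintenance upadacitinib.
- 45 mg responder re-randomised to placebo (Cohort 1): counted under maintenance placebo, and outside SA_UPA unless upadacitinib is taken in maintenance.
- Subject who receives no further study treatment after induction: counted under induction for 30 days.

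Only the second group loses the link to upadacitinib.

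**3. Size of that group**

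Inputs: 450 subjects re-randomised 1:1:1, with 150 on placebo (Protocol Section 8.2; Substudy 3 SAP Section 2.4), and 52 weeks = 364 days of maintenance.

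- Placebo: 450 / 3 = 150 (33%). Upadacitinib: 450 − 150 = 300 (67%).
- Person-time in the first 30 days on placebo: 150 × 30 / 365.25 = 12.3 patient-years.
- Full planned placebo exposure: 150 × 364 / 365.25 = 149.5 patient-years.
- Share: 30 / 364 = 8.2%.

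The documents give no expected mean placebo exposure. Assuming 39 weeks (273 days), the share is 30 / 273 = 11%. Assuming 26 weeks (182 days), it is 30 / 182 = 16%.

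**The case against.** The best defence is that the per-period windows are what the protocol asks for. Section 8.1.8.2.1 defines treatment-emergent events by period of the study, and a responder on blinded placebo is still taking study medication, so the 30-day clock in Section 8.1.8.1 has not started. This stands. The per-substudy tables are legitimate, and a reader should not infer that the protocol requires events to be carried back across the boundary. The per-period tables do not, however, replace the entire-study tables that the protocol promises separately.

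A second defence is that every SA_A arm arrives from 45 mg, so early events caused by that dose are a background shared by the randomised arms. This also stands. The comparison remains a fair one between maintenance regimens after 45 mg. What it does not give in the first month is a placebo rate free of recent upadacitinib. The events are not lost either: they appear in the SA_A and SA_C tables, and serious events and events of special interest are listed.

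Third, each SAP limits itself to its own substudy, so the statement that nothing else is planned may mean only that. This limits the inference but does not answer it, because Section 8.1 of the protocol names no other place for the details. The Substudy 3 SAP (Section 9.1) already crosses the boundary for laboratory and vital-sign shift and threshold analyses by using a pre-upadacitinib induction baseline. It does not do so for adverse events.

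**Conclusion.** The point holds as a gap between protocol and SAPs, with one limited consequence for attribution. The entire-study safety and exposure analysis is committed to in the protocol and specified in none of the three SAPs, and its removal is not recorded in the Substudy 2 or 3 SAP. Separately, events within 30 days of 45 mg in about 150 of 450 subjects are counted only under maintenance placebo. That is about 12.3 patient-years, or 8.2% of placebo exposure if everyone completes 52 weeks. The figures rest on planned sizes and treat the first 30 maintenance days as the 30 days after the last 45 mg dose.

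Three stronger readings are not supported:

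- A reader might infer that all events after 45 mg count against placebo. About two thirds of the main Cohort 1 group, and all of Cohort 3, have them counted under upadacitinib.
- A reader might infer that cumulative rates will never be produced. The documents show only that no SAP supplied here specifies them; an integrated analysis elsewhere cannot be excluded. For subjects from M14-675, that study's own analysis plan is not among the documents.
- A reader might argue that particular risks depend on cumulative dose. The documents give no basis for that, and the point does not need it.

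**What to change.** In the Substudy 3 SAP (Sections 4.0, 9.1, 9.2.1 and 10.0):

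1. Define the union safety set of all subjects treated in Substudies 1 to 3.
2. Add entire-study exposure, and counts and rates per 100 patient-years for treatment-emergent events, serious events, deaths and events of special interest. Run upadacitinib time from the first upadacitinib dose to 30 days after the last upadacitinib dose, or to the first M14-533 dose.
3. Keep the per-period tables as they are. Add a supplementary split of maintenance placebo-arm events at day 30 after the last induction upadacitinib dose.
4. State how M14-675 induction exposure is handled: include all treated M14-675 subjects or none. Including only those who entered Substudy 3 would select subjects who completed induction and responded, and would bias the rates downward.

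If the sponsor prefers not to do the entire-study analysis, its removal and the reason should be recorded in Section 13.0.

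The cost is SAP wording and one extra set of tables. No new data are needed, and efficacy testing and its alpha are untouched. The safety-only update planned once all subjects have completed (Substudy 3 SAP, Section 2.3) is a natural place to report it.

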1.3 List of Abbreviations and Definition of Terms

Abbreviations

6-MP	6-mercaptopurine
6-TGN	6-thioguanine
AD	Atopic dermatitis
AE	Adverse Event
ALC	Absolute Lymphocyte Count
ALT	Alanine Transaminase
ANCOVA	Analysis of Covariance
ANOVA	Analysis of Variance
AST	Aspartate Transaminase
AUC	Area under the plasma concentration-time curve
AZA	Azathioprine
ATEMS	AbbVie Temperature Excursion Management System
BCG	Bacille Calmette-Guérin
BID	Twice daily
BMI	Body Mass Index
BP	Blood pressure
BUN	Blood Urea Nitrogen
CAC	Cardiovascular Adjudication Committee
CD	Crohn's Disease
CDC	Centers for Disease Control and Prevention
CD4, CD8	Cluster of Differentiation
CFR	Code of Federal Regulations
CGC	Common Gamma-Chain
CI	Confidence Interval
CL/F	Oral Clearance
C _{max}	Maximum Observed Plasma Concentration
CMH	Cochran-Mantel-Haenszel
CNS	Central Nervous System
COVID-19	Coronavirus Disease - 2019
CPK	Creatine Phosphokinase
CR	Clinical Remission

CRA	Clinical Research Associate
CRF	Case Report Form
CRP	C-Reactive Protein
C _{min}	Minimum Plasma Concentration During a Dosing Interval
CT	Computed Tomography
CTCAE	Common Terminology Criteria for Adverse Events
CXR	Chest X-Ray
CYP3A	Cytochrome P450 3A
DMARD	Disease-Modifying Anti-Rheumatic Drug
DMC	Data Monitoring Committee
DNA	Deoxyribonucleic Acid
DTP	Direct-to-patient
ECG	Electrocardiogram
eCRF	Electronic Case Report Form
EDC	Electronic Data Capture
EIMs	Extra-Intestinal Manifestations
EMA	European Medicines Agency
EMA	European Agency for the Evaluation of Medicinal Products
ePRO	Electronic Patient Reported Outcomes
EQ-5D-5L	European Quality of Life-5 Dimensions 5 Levels
ER	Extended Release
FACIT-F	Functional Assessment of Chronic Illness Therapy – Fatigue
FDA	US Food and Drug Administration
FSH	Follicle-stimulating Hormone
GCP	Good Clinical Practice
GI	Gastrointestinal
gp130	Glycoprotein 130
GPRD	Global Pharmaceutical Research and Development
HBc Ab	Hepatitis B Core Antibody
HBs Ab	Hepatitis B Surface Antibody
HBs Ag	Hepatitis B Surface Antigen
HBV	Hepatitis B virus
HCRU	Health Care Resource Utilization
HCV	Hepatitis C Virus

HCV Ab	Hepatitis C Virus Antibody
HDL-C	High Density Lipoprotein Cholesterol
HIV	Human Immunodeficiency Virus
HIV Ab	Anti-HIV antibody
HCRU	Health Care Resource Utilization
hs-CRP	High-Sensitivity C-Reactive Protein
IBD	inflammatory bowel disease
IBDQ	Inflammatory Bowel Disease Questionnaire
IC	Indeterminate Colitis
ICF	Informed Consent Form
ICH	International Conference on Harmonisation of Technical Requirements for Registration of Pharmaceuticals for Human Use
IEC	Independent Ethics Committee
IgM	Immunoglobulin M
IGRA	Interferon-Gamma Release Assay
IL	Interleukin
IMP	Investigational Medicinal Product
INR	International Normalized Ratio
IR	Immediate Release
IRB	Institutional Review Board
IRT	Interactive Response Technology
ITT	Intent-to-Treat
IUD	Intrauterine Device
IUS	Intrauterine Hormone-Releasing System
IV	Intravenously
JAK	Janus Activated Kinase
LDL-C	Low Density Lipoprotein Cholesterol
LOCF	Last Observation Carried Forward
MACE	Major Adverse Cardiovascular Event
MCP-Mod	Multiple Comparison Procedure – Modeling
MCS	Mental Component Summary
MDRD	Modification of Diet in Renal Disease
MED	Minimum Effective Dose
MedDRA	Medical Dictionary for Regulatory Activities
MMRM	Mixed Effect Repeated Measure

MTX	Methotrexate
NCI	National Cancer Institute
NK	Natural Killer Cells
NKT	Natural Killer T-Cells
NOAEL	No Observable Adverse Effect Level
NMSC	Nonmelanoma Skin Cancer
NRI	Non-Responder Imputation
NRI-C	Non-Responder Imputation while incorporating Multiple Imputation (MI) to handle missing data due to COVID-19
NSAID	Non-Steroidal Anti-Inflammatory Drug
OC	Observed Cases
PCR	Polymerase Chain Reaction
PCS	Physical Component Summary
PD	Premature Discontinuation
PGA	Physician's Global Assessment
PGIC	Patient Global Impression of Change
PGIS	Patient Global Impression of Severity
PK	Pharmacokinetic
PPD	Purified Protein Derivative
PRO	Patient Reported Outcomes
PsA	Psoriatic arthritis
QTcF	QT Interval Corrected for Heart Rate by Fridericia's Correction Formula
RA	Rheumatoid Arthritis
RAVE®	EDC System from Medidata
RBC	Red Blood Cell Count
RNA	Ribonucleic Acid
RBS	Rectal Bleeding Subscore
RSI	Reference Safety Information
SAE	Serious Adverse Event
SAP	Statistical Analysis Plan
SC	Subcutaneous
SF-36	Short Form 36
SFS	Stool Frequency Subscore
SOC	System Organ Class
STAT	Signal Transduction Activators of Transcription

SUSAR	Suspected Unexpected Adverse Reactions
TA MD	Therapeutic Area Medical Director
TB	Tuberculosis
TEAE	Treatment-Emergent Adverse Event
TNF	Tumor Necrosis Factor
TPN	Total Parenteral Nutrition
UC	Ulcerative Colitis
UCEIS	Ulcerative Colitis Endoscopic Index of Severity
UC-SQ	Ulcerative Colitis Symptoms Questionnaire
ULN	Upper Limit of Normal
US	United States
V/F	Volume of Distribution
VAS	Visual Analogue Scale
WBC	White Blood Cell Count
WHO	World Health Organization
WPAI	Work Productivity and Impairment Questionnaire

Definition of Terms

Bio-IR	Biologic inadequate responders: inadequate response, loss of response, or intolerance to biologic therapy
Non-bio-IR	Non-biologic-inadequate responders: inadequate response, loss of response, or intolerance to conventional therapy but have not failed biologic therapy

3.0 Introduction

Ulcerative colitis (UC) is one of the two primary forms of idiopathic inflammatory bowel disease (IBD). It is postulated that UC is caused by unregulated and exaggerated local immune response to environmental triggers in genetically susceptible individuals.¹ UC is a chronic, relapsing inflammatory disease of the large intestine characterized by inflammation and ulceration of mainly the mucosal and occasionally submucosal intestinal layers. The highest annual incidence of UC was 24.3 per 100,000 person-years in Europe, 6.3 per 100,000 person-years in Asia and the Middle East, and 19.2 per 100,000 person-years in North America, with a prevalence of 505 cases per 100,000 persons in Europe and 249 cases per 100,000 persons in North America.² The burden of UC on the healthcare system is profound, accounting for nearly 500,000 physician visits and more than 46,000 hospitalizations per year in the United States (US) alone.³

The hallmark clinical symptoms include bloody diarrhea associated with rectal urgency and tenesmus. The clinical course is marked by exacerbation and remission. The diagnosis of UC is suspected on clinical grounds and supported by diagnostic testing, and elimination of infectious causes.⁴

The most severe intestinal manifestations of UC are toxic megacolon and perforation. Extraintestinal complications include arthritis (peripheral or axial involvement), dermatological conditions (erythema nodosum, aphthous stomatitis, and pyoderma gangrenosum), inflammation of the eye (uveitis), and liver dysfunction (primary sclerosing cholangitis). Patients with UC are at an increased risk for colon cancer, and the risk increases with the duration of disease as well as extent of colon affected by the disease.⁵

The aim of medical treatment in UC is to control inflammation and reduce symptoms. Available pharmaceutical therapies are limited, do not always completely abate the inflammatory process, and may have significant adverse effects. Therapies for mild to moderate active UC include 5-aminosalicylic acid derivatives and immunosuppressants.

Corticosteroids are used in patients with more severe symptoms but are not useful for longer term therapy.⁶ The frequency and severity of corticosteroid toxicities are significant, including infections, emotional and psychiatric disturbances, skin injury, and metabolic bone disease. Corticosteroids are not effective for the maintenance of remission and the UC practice guidelines from the American College of Gastroenterology recommend against chronic steroid treatment.⁷ Patients with moderate to severe symptoms may derive some benefits from immunomodulatory agents (azathioprine [AZA], 6-mercaptopurine [6-MP], or methotrexate [MTX]); however, the use of these agents is limited as induction treatment due to a slow onset of action (3 to 6 months) and as maintenance therapy due to adverse events (AEs), including bone marrow suppression, infections, hepatotoxicity, pancreatitis, and malignancies.^{7,8} Despite these therapies, approximately 15% of UC patients experience a severe clinical course, and 30% of these patients require removal of the colon/rectum, to eliminate the source of the inflammatory process, although accompanied by significant morbidity.^{9,10}

Biological agents targeting specific immunological pathways have been evaluated for their therapeutic effect in treating patients with UC. Anti-tumor necrosis factor (TNF) agents were the first biologics to be used for IBD. Infliximab, adalimumab, and golimumab are successfully being used for the treatment of UC. Vedolizumab, an anti-adhesion therapy, has been approved for the treatment of IBD.

Anti-TNF therapies are an effective treatment for patients who are steroid refractory or steroid dependent, who had inadequate response to a thiopurine, or who are intolerant to these medications. Potential risks with anti-TNF therapies include infusion or injection site reactions, serious infections, lymphoma, heart failure, lupus-like syndromes, and demyelinating conditions.¹¹ Despite the beneficial results achieved with the available biologic agents, only 17% to 45% of patients who receive them are able to achieve clinical remission.¹²⁻¹⁵ Thus, there remains a clear medical need for additional therapeutic options in UC for patients with inadequate response to or intolerance to conventional therapies and biologic therapies.

Rationale for Development of a JAK Inhibitor in UC

The Janus kinases or JAKs are a family of intracellular tyrosine kinases that function as dimers in the signaling process of many cytokine receptors. The JAKs play a critical role in both innate and adaptive immunity, making them attractive targets for the treatment of inflammatory diseases. Targeting the Janus activated kinase (JAK) signaling pathway for autoimmune diseases is supported by the involvement of various pro-inflammatory cytokines that signal via JAK pathways in the pathogenesis of these immune-related disorders. The activation of JAK signaling initiates expression of survival factors, cytokines, chemokines, and other molecules that facilitate leukocyte cellular trafficking and cell proliferation, which contribute to inflammatory and autoimmune disorders.¹⁶

Tofacitinib is an oral JAK inhibitor that inhibits JAK1, JAK2 and JAK3 with high in vitro functional specificity for kinases 1 and 3. In completed Phase 3 studies in patients with moderately to severely active UC, tofacitinib was more effective than placebo as induction and maintenance therapy.¹⁷

JAK inhibitors have been associated with infections, including herpes zoster reactivation, malignancies, and asymptomatic, mild and reversible changes in levels of hemoglobin, lymphocyte counts, white blood cell counts, serum creatinine, total cholesterol, high density lipoprotein cholesterol (HDL-C), low density lipoprotein cholesterol (LDL-C) and liver transaminases (alanine transaminase [ALT], aspartate transaminase [AST]) and creatine phosphokinase (CPK).^{18,19}

Upadacitinib is a novel selective Janus kinase (JAK) 1 inhibitor. JAK1 inhibition blocks the signaling of many important pro-inflammatory cytokines, including interleukin (IL)-2, IL-6, IL-7, and IL-15, which are known contributors to inflammatory disorders. Through modulation of these proinflammatory cytokine pathways, upadacitinib offers the potential for effective treatment of inflammatory or autoimmune disorders such as rheumatoid arthritis (RA), psoriatic arthritis (PsA), axial spondyloarthritis (axSpA), giant cell arteritis (GCA), Takayasu arteritis, polyarticular course juvenile idiopathic arthritis (pcJIA), Crohn's disease (CD), UC and atopic dermatitis (AD). The clinical hypothesis is that,

based on the differentiated selectivity profile for JAK inhibition, upadacitinib could demonstrate an improved benefit/risk profile compared to other less selective JAK inhibitors or other therapeutic strategies for patients with inflammatory diseases.

To date, upadacitinib has been investigated in 22 Phase 1 studies with healthy volunteers (one of which also employed a substudy in subjects with mild to moderate RA), and multiple Phase 2 or Phase 3 studies for indications of RA, CD, AD, PsA and UC. Upadacitinib has been shown to be effective in the treatment of the indicated medical conditions based on the data available from the various studies. Safety results across the studies showed that upadacitinib was well tolerated and the types and frequencies of AEs were consistent with subjects with the medical conditions receiving immunomodulatory therapy. Many of the safety findings are expected for the class products with JAK inhibition, such as infections, increase in LDL-C and HDL-C, and asymptomatic and transient CPK elevation.

Upadacitinib has been evaluated in Phase 2b dose ranging placebo-controlled study in subjects with moderately to severely active UC with a history of inadequate response to or intolerant to immunosuppressants, corticosteroids or biologic therapies (Study M14-234 Substudy 1). At the time of this amendment, Phase 2b interim results from this Study M14-234 Substudy 1 Part 1 became available. The primary objective of demonstrating statistically significant dose-response relationship of upadacitinib compared to placebo for the primary endpoint and all ranked secondary endpoints was met, with the highest rates observed in the 45 mg once daily (QD) treatment group for both clinical and endoscopic endpoints. Upadacitinib was generally safe and well tolerated. No new safety concerns were identified compared to what has been observed in studies of upadacitinib in other disease indications.

A detailed discussion of the preclinical toxicology, metabolism, pharmacology and safety experience with upadacitinib can be found in the current Investigator's Brochure.²⁰

